6. CONCOMITANT THERAPIES AND OTHER RESTRICTIONS

6.1. Concomitant Therapy

Any medication or vaccine (including over-the-counter or prescription medicines, vitamins, and/or herbal supplements) that the subject is receiving at the time of ICF signing onwards must be recorded along with:

- reason for use
- dates of administration including start and end dates
- dosage information including dose and frequency

The medical monitor should be contacted if there are any questions regarding concomitant or prior therapy.

Any medications, excluding those mentioned in Section 6.1.1, may be given concomitantly as needed for the subject's welfare for treatment of comorbid conditions or potential AEs.

At each visit in this study, the study staff will review use of concomitant medications with the subject and will record entries in the eCRF.

6.1.1. Prohibited Concomitant Therapy

Subjects may not be on the following drugs from the time of ICF signing onwards:

- PDE-5 inhibitors (e.g., Viagra, Cialis, Revatio, and Adcirca)
- Known strong inhibitors or inducers of CYP3A4.

6.1.2. Contraception

6.1.2.1. Female Subjects

Female subjects of childbearing potential, as defined in Inclusion Criterion #6, will be required to follow contraception requirements as defined in Inclusion Criterion #7.

6.1.2.2. Male Subjects

Male subjects with female partners of child-bearing potential, or female partners who are pregnant will be required to follow contraception requirements as defined in Inclusion Criterion #8.

6.1.2.3. Sexual Abstinence and Same-sex Relationships

Subjects who practice true abstinence, which must be due to the subject's lifestyle choice (i.e., the subject should not become abstinent just for the purpose of study participation), are exempt from contraceptive requirements. Periodic abstinence (e.g., calendar, ovulation, symptothermal,

FINAL 10 AUG 2022 Page 47 of 73

post-ovulation methods) and withdrawal are not acceptable methods of contraception. If a subject who is abstinent at the time of signing the ICF becomes sexually active, they must agree to use contraception as described previously.

For subjects who are exclusively in same-sex relationships, contraceptive requirements do not apply. If a subject who is in a same-sex relationship at the time of signing the ICF becomes engaged in a heterosexual relationship, they must agree to use contraception as described previously.

FINAL 10 AUG 2022 Page 48 of 73

CONFIDENTIAL Sponsor Reference: CRD-740-201

7. STUDY ASSESSMENTS AND PROCEDURES

Study procedures and their timing are summarized in the Schedule of Assessments (Appendix 4). Adherence to the study design requirements, including those specified in the Schedule of Assessments (Appendix 4), is essential and required for study conduct.

[figure not shown]
All screening evaluations must be completed and reviewed to confirm that potential subjects meet all eligibility criteria. The investigator will maintain a screening log to record details of all subjects screened and to confirm eligibility or record reasons for screening failure (Section 4.3.1), as applicable.

All laboratory tests in this study will be performed at a central laboratory.

The maximum amount of blood collected from each subject over the duration of the study will be in line with local regulations. Repeat or unscheduled samples may be taken for safety reasons or for technical issues with the samples.

Please refer to the study-specific safety guidance documents for detailed safety requirements of this study.

7.1. Efficacy Assessments

7.1.4. Plasma cGMP

Plasma cGMP will be assessed at the time-points specified in the Schedule of Assessments (Appendix 4).

7.1.5. Urinary cGMP

In Part A of this study only, urinary cGMP (6-hour urine collection and spot urine) will be assessed at the time-points specified in the Schedule of Assessments (Appendix 4).

FINAL 10 AUG 2022 Page 49 of 73

7.2. Safety and Tolerability Assessments

7.2.1. Adverse Events

AE definitions and assignment of severity and causality are detailed in Appendix 1.

AEs will be elicited from the subject (or, when appropriate, from a caregiver, surrogate, or the subject's legally authorized representative) by the study site staff using a non-leading question such as "How are you feeling today?" or "Have you had any health concerns since your last visit?" Subjects will be encouraged to voluntarily report AEs occurring at any time during the study. AEs will be recorded in the eCRF.

The investigator and any designees are responsible for detecting, documenting, and reporting events that meet the definition of an AE or SAE and remain responsible for following up on AEs that are serious, considered related to the study drug or the study, or that caused the subject to discontinue the study drug or study. For all AEs, the investigator must pursue and obtain information to determine the causality and outcome of the AE and to assess whether it meets the criteria for classification as an SAE requiring immediate notification to the sponsor or its designee.

7.2.2. Reporting Serious Adverse Events

Please refer to the study-specific safety guidance documents for the appropriate methods for the reporting and handling of SAEs.

7.2.3. Pregnancy

If a female subject becomes pregnant during the study, the study drug must be discontinued immediately. During the study, pregnancy events should be reported and will be followed until conclusion. Please refer to the study-specific safety guidance documents for details.

7.2.4. Laboratory Safety Tests

At the time-points specified in the Schedule of Assessments (Appendix 4) and at all unscheduled visits as applicable, blood and urine samples will be collected for laboratory safety tests, including hematology, biochemistry, coagulation, and urinalysis. Please refer to Appendix 2 for the analytes of each laboratory test. Clinically significant laboratory abnormalities, in the opinion of the investigator, should be reported as AEs.

7.2.5. Vital Signs

Vital signs, including heart rate, blood pressure (systolic and diastolic), respiratory rate, and temperature will be measured at the time-points specified in the Schedule of Assessments (Appendix 4) and at all unscheduled visits as applicable. Vital sign measurements will be recorded with the subject in a seated position and after the subject has been resting for at least 5 minutes. All measurements will be performed singly. For any abnormal vital sign finding, further assessment should be performed as deemed necessary by the investigator. In case of rescreening, all vital sign parameters will be rechecked as described above.

FINAL 10 AUG 2022 Page 50 of 73

7.2.6. Physical Examination

Physical examination will include assessment of heart, lung, extremities, body weight, and height. Height will only be assessed at screening. Body weight will be assessed at screening and on Day 85 (Visit 9 of Part A at the time-points specified in the Schedule of Assessments (Appendix 4) and at all unscheduled visits as applicable. Clinically significant changes from the initial physical findings at screening observed in subsequent visits will be considered AEs and will be documented on the AE section of the eCRF.

7.2.7. 12-lead Electrocardiogram

Resting 12-lead ECGs will be recorded after the subject has been supine and at rest for at least 5 minutes at the time-points specified in the Schedule of Assessments (Appendix 4) and at all unscheduled visits as applicable.

7.3. Pharmacokinetic Analysis

7.3.1. Pharmacokinetic Blood Sample Collection and Processing

Blood samples for analysis of CRD-740 concentrations will be collected by venipuncture at the time-points specified in the Schedule of Assessments (Appendix 4). Procedures for collection, processing, and shipping of PK blood samples will be detailed in the laboratory manual. PK samples will be assessed at a central laboratory.

7.3.2. Analytical Methodology

Plasma concentration of CRD-740 will be determined using a validated analytical procedure. Specifics of the analytical method will be provided in the bioanalytical report.

FINAL 10 AUG 2022 Page 51 of 73

8. SAMPLE SIZE AND DATA ANALYSES

8.1. Determination of Sample Size

In Part A, approximately 60 subjects with CHFrEF will be included.

[figure not shown]
The sample size was not determined by power calculations but by considerations to provide a reasonable number of subjects to assess the study objectives. Table 3 below summarizes the Part A sample sizes.

Table 3: Part A, dose ranging, sample sizes, no caps

[figure not shown]
EF%, Entresto	Randomized (2:1) Treatment	Sample Size		
≤40, Yes	CRD-740	² ∕ ₃ n ₁		
≤40, Yes	Placebo	½ n ₁		
≤40, No	CRD-740	² ∕ ₃ n ₂		
≤40, No	Placebo	¹∕₃ n₂		
	Total N	60		

Note: $n_1 + n_2 = 60$, where n_1 and n_2 are unknown and random; they denote the number of CHFrEF subjects with and without Entresto use, respectively. Randomization will be stratified on Entresto use (yes, no) and employ a 2:1 randomization ratio (CRD-740: Placebo) within each stratum.

Abbreviations: CHFrEF = chronic heart failure with reduced ejection fraction; EF = ejection fraction

FINAL 10 AUG 2022 Page 52 of 73

8.2. Analysis Populations

The following analysis populations will be included for this study:

Intention to Treat (ITT): The ITT population consists of all randomized subjects. Subjects will be analyzed according to their randomized treatment, regardless of actual treatment received, treatment compliance, or treatment duration. The ITT population will be used for sensitivity analyses.

Modified ITT (mITT): The mITT population consists of all randomized subjects who received at least one dose of CRD-740 or placebo. Subjects will be analyzed according to their randomized treatment, regardless of actual treatment received, treatment compliance, or treatment duration. The mITT population will be used as the primary efficacy population.

Safety: The Safety population consists of all subjects who received at least one dose of CRD-740 or placebo. Subjects will be analyzed according to the treatment first received. The Safety population will be used as the primary safety population.

Pharmacokinetic: The PK population consists of all subjects who received at least one dose of CRD-740 and have no protocol deviations that are considered to impact the PK results.

Per protocol (PP): The PP population consists of all mITT subjects with no important protocol deviations. Subjects will be analyzed according to their randomized treatment. The PP population will be used for sensitivity analyses.

8.3. General Considerations

In general, data will be summarized with descriptive statistics for continuous endpoints, and frequency and percentage for categorical endpoints, unless otherwise specified. Percentages by

FINAL 10 AUG 2022 Page 53 of 73

CONFIDENTIAL Sponsor Reference: CRD-740-201

categories will be based on the number of subjects with no missing data (i.e., will add up to 100%).

Baseline will be defined as the last non-missing observation prior to first treatment intake, unless otherwise specified.

8.4. Efficacy Analysis

[figure not shown]
8.4.1. Primary Efficacy Outcome Measures

Part A

[figure not shown]
The primary endpoint is the change from baseline (Day -1) in plasma cGMP at Week 4. It will be compared between CRD-740 and placebo in the mITT population using an analysis of covariance (ANCOVA) model with categorical terms for treatment (2 levels), and Entresto (2 levels), and continuous terms for EF, and baseline plasma cGMP.

CRD-740 will be analyzed as one treatment group even though CRD-740 consists of two weeks of treatment with CRD-40 , followed by two weeks of treatment with CRD-740

[figure not shown]
The least square means of the change from baseline for each treatment group, along with the 95% confidence intervals (CI), and the least square mean treatment difference and the associated 95% CI for this difference will come from the ANCOVA model.

FINAL 10 AUG 2022 Page 54 of 73

FINAL 10 AUG 2022 Page 55 of 73

8.5. Safety Analysis

All safety data will be summarized, by treatment group and dose period (Period 1, Period 2, Period 3, pooled Period 2 and Period 3, and overall) for Part A and by treatment group for Part B in the Safety Data Set.

For Part A, the primary safety analysis will be performed by reporting the exposure-adjusted incidence rates in subject-years for AE and SAE defined as the number of subjects with that particular AE or SAE within a system organ class or preferred term during the relevant period divided the sum of the at-risk times. The total at risk time is the sum of exposure time in each period in years. The adjusted incidence rates will be presented by system organ class and preferred term for Period 1, and separately for Periods 2 and 3 combined. The Hodges-Lehmann methodology will be used to estimate the within-subject point and interval treatment difference.

FINAL 10 AUG 2022 Page 56 of 73

Adverse events

For both Part A and Part B, global incidence of emergent adverse events (EAE) (i.e., all events occurring, worsening or becoming serious after the first study treatment intake) will be given by system organ class and preferred term according to the Medical Dictionary of Regulatory Activities.

The same description will be performed for serious EAE, severe EAE, treatment related EAE, and EAE leading to study drug withdrawal.

AEs leading to death will also be summarized.

Vital signs / Physical examination

For both Part A and Part B, descriptive statistics will be performed on observed values at each visit and on each change and relative change from baseline.

Box plots will be produced for some pre-selected vital signs.

ECG abnormalities

For both Part A and Part B, quantitative routine 12-lead ECG results will be summarized on observed values at each visit and on each change and relative change from baseline.

Box plots will be produced for some pre-selected ECGs.

12-lead ECG data interpretations and quantitative values will be listed.

Laboratory tests

For both Part A and Part B, descriptive statistics will be performed on observed values at each visit and on each change and relative change from baseline.

The number and percentage of subjects having a value out of reference laboratory range (respectively out of potentially clinically significant range) will also be provided.

Box plots will be produced for some pre-selected lab parameters.

8.6. Pharmacokinetic Analysis

PK parameters will be calculated with plasma concentrations of CRD-740 in Part A using non-compartmental methods.

Details of PK data handling, analysis methodology, and reporting will be included in the SAP.

All plasma concentrations of CRD-740 will be summarized by study part, dose, visiting day, and time-points. PK parameters will be summarized for Part A by dose and visiting day.

FINAL 10 AUG 2022 Page 57 of 73

10. APPENDICES

FINAL 10 AUG 2022 Page 59 of 73

Appendix 1 – Adverse Event Definitions

Definitions

An adverse event (AE) is any untoward medical occurrence associated with the use of a drug in humans, whether or not considered drug related. This includes the following:

- Any clinically significant worsening of a pre-existing condition.
- Any recurrence of a pre-existing condition.
- An AE occurring from overdose of a sponsor study drug whether accidental or intentional (i.e., a dose higher than that prescribed by a health care professional for clinical reasons).
- An AE occurring from abuse of a sponsor study drug (i.e., use for non-clinical reasons).
- An AE that has been associated with the discontinuation of the use of a sponsor study drug.

Note: A procedure is not an AE, but the reason for a procedure may be an AE.

A pre-existing condition is a clinical condition (including a condition being treated) that is diagnosed before the subject signs the informed consent form and that is documented as part of the subject's medical history.

The questions concerning whether the condition existed before the start of the active phase of the study and whether it has increased in severity and/or frequency will be used to determine whether an event is a treatment-emergent AE. An AE is considered to be treatment-emergent if (1) it is not present when the active phase of the study begins and is not a chronic condition that is part of the subject's medical history, or (2) it is present at the start of the active phase of the study or as part of the subject's medical history, but the severity or frequency increases during the active phase. The active phase of the study begins at the time of the first dose of the study drug. The active phase of the study ends at the follow-up visit.

Reporting of Adverse Events

At each visit, the investigator, or delegate, will determine whether or not any AEs have occurred. Non-leading questions such as "How are you feeling today?" or "Have you had any health concerns since your last visit?" should be used to elicit the subject (or, when appropriate, from a caregiver, surrogate, or the subject's legally authorized representative) to report any possible AEs. If any AEs have occurred, they will be recorded in the AE section of the electronic case report form (eCRF) and in the subject's source documents. If known, the diagnosis should be recorded, in preference to listing the individual signs and symptoms.

AE reporting begins from the time of informed consent and ends 28 days after the last dose of study drug.

FINAL 10 AUG 2022 Page 60 of 73

Assessment of Severity

The investigator will be asked to provide an assessment of the severity of the AE using the following categories:

- **Mild**: Usually transient and may require only minimal treatment or therapeutic intervention. The event does not generally interfere with usual activities of daily living.
- **Moderate**: Usually alleviated with additional specific therapeutic intervention. The event interferes with usual activities of daily living, causing discomfort but poses no significant or permanent risk of harm to the subject.
- **Severe**: Interrupts usual activities of daily living, significantly affects clinical status, or may require intensive therapeutic intervention.

Relationship to Study Drug

The investigator will make a determination of the relationship of the AE to the study drug using a binary system according to the following guidelines:

- **Related**: There is a reasonable possibility that the drug causes the AE.
- **Not related**: There is no reasonable possibility that the drug causes the AE.

Action Taken for Adverse Events

The investigator or his/her designee will record the action taken for the AE in the eCRF. Actions taken will include:

- **Dose not changed**: The medication schedule was not changed.
- **Drug interrupted**: The medication schedule was modified by temporarily terminating the prescribed regimen of medication.
- **Drug withdrawn**: The medication schedule was modified through termination of the prescribed regimen of medication.
- Not applicable
- Unknown

Follow-up of Adverse Events

All AEs or serious adverse events (SAEs) that are ongoing at the time of discontinuation, or that develop prior to the final follow-up visit, will be followed for 28 days, or until resolution or stabilization.

FINAL 10 AUG 2022 Page 61 of 73

Adverse Drug Reactions

All noxious and unintended responses to an investigational medicinal product (IMP; i.e., where a causal relationship between an IMP and an AE is a reasonable possibility) related to any dose should be considered adverse drug reactions.

For marketed medicinal products, a response to a drug which is noxious and unintended and which occurs at doses normally used in man for prophylaxis, diagnosis, or therapy of diseases or for modification of physiological function is to be considered an adverse drug reaction.

An unexpected adverse drug reaction is defined as an adverse reaction, the nature or severity of which is not consistent with the applicable product information (e.g., investigator's brochure for an unapproved IMP).

Serious Adverse Events

An SAE is any AE occurring at any dose that meets 1 or more of the following criteria:

- Results in death
- Is life threatening (see below)
- Requires subject hospitalization or prolongation of an existing hospitalization (see below)
- Results in a persistent or significant disability or incapacity (see below)
- Results in a congenital anomaly or birth defect
- Results in an important medical event (see below).

Additionally, important medical events that may not result in death, be life threatening, or require hospitalization may be considered SAEs when, based on appropriate medical judgment, they may jeopardize the subject and may require medical or surgical intervention to prevent one of the outcomes listed above. Examples of such events include allergic bronchospasm requiring intensive treatment in an emergency room or at home, blood dyscrasias, or convulsions that do not require hospitalization, or development of drug dependency or drug abuse.

A *life-threatening AE* is any AE that places the subject at immediate risk of death from the event as it occurred. A life-threatening event does not include an event that might have caused death had it occurred in a more severe form but that did not create an immediate risk of death as it actually occurred. For example, drug-induced hepatitis that resolved without evidence of hepatic failure would not be considered life threatening, even though drug-induced hepatitis of a more severe nature can be fatal. Hospitalization is to be considered only as an overnight admission.

Hospitalization or prolongation of a hospitalization is a criterion for considering an AE to be serious. In the absence of an AE, the participating investigator should not report hospitalization or prolongation of hospitalization. This is the case in the following situations:

FINAL 10 AUG 2022 Page 62 of 73

 Hospitalization or prolongation of hospitalization is needed for a procedure required by the protocol. Day or night survey visits for biopsy or surgery required by the protocol are not considered serious.

- Hospitalization or prolongation of hospitalization is part of a routine procedure followed by the study center (e.g., stent removal after surgery). This should be recorded in the study file.
- Hospitalization for survey visits or annual physicals fall in the same category.

In addition, a hospitalization planned before the start of the study for a pre-existing condition that has not worsened does not constitute an SAE (e.g., elective hospitalization for a total knee replacement due to a pre-existing condition of osteoarthritis of the knee that has not worsened during the study).

Disability is defined as a substantial disruption in a person's ability to conduct normal life functions (i.e., the AE resulted in a significant, persistent, or permanent change, impairment, damage, or disruption in the subject's bodily function/structure, physical activities, or quality of life).

Medical and scientific judgment should be exercised in deciding whether a case is serious in those situations where important medical events may not be immediately life threatening or result in death, hospitalization, disability, or incapacity. These include events that may jeopardize the subject or may require medical intervention to prevent one or more outcomes listed in the definition of serious. Such events should usually be considered as serious.

FINAL 10 AUG 2022 Page 63 of 73

Protocol Labcorp Study: 8459270 CONFIDENTIAL Sponsor Reference: CRD-740-201

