Appendix 4 - Schedule of Assessments

1. Schedule of Assessments for Part A

Visit	1	2	3	4	5	6	7	8	9	10
				(remote°)		(remote°)		(remote°)		(remote°)
Assessment ^a	Screening ^b (Day -15 to Day -2)	Day -1	Day 1	Day 3 (±1 day)	Day 15 (Week 2) (±2 days)	Day 17 (±1 day)	Day 29 (Week 4) (+3 days)	Day 57 (Week 8) (±5 days)	Day 85 or ET (Week 12) (±5 days)	Day 113 (Week 16) (-2/+5 days)
Informed consent	X									
Inclusion/exclusi on criteria	X									
Demographic data	X									
Medical history	X									
Serum pregnancy test ^c	X									
Urine pregnancy test ^c			X		X		X		X	
FSH d	X									
Vital signs e	X		X		X		X		X	
Physical examination ^f	X		X		X		X		X	
12-lead ECG g	X		X		X		X		X	
									1)	
Randomization		X								
Coagulation panel (aPTT, PT, INR)	X									
Laboratory safety tests ⁱ	X		X	X	X	X	X	X	X	
Study drug administration ^j			X	X	X	X	X	X	_	

FINAL 10 AUG 2022 Page 69 of 73

Visit	1	2	3	4	5	6	7	8	9	10
				(remote°)		(remote°)		(remote°)		(remote°)
Assessment ^a	Screening ^b (Day -15 to Day -2)	Day -1	Day 1	Day 3 (±1 day)	Day 15 (Week 2) (±2 days)	Day 17 (±1 day)	Day 29 (Week 4) (+3 days)	Day 57 (Week 8) (±5 days)	Day 85 or ET (Week 12) (±5 days)	Day 113 (Week 16) (-2/+5 days)
Drug accountability			X		X		X		X	
Dose escalation					X					
AE recording	X	X	X	X	X	X	X	X	X	X
Concomitant medications	X	X	X	X	X	X	X	X	X	X
Blood sample for drug assay (PK)			X ^k (pre-dose, 1 hr, 2 hr, 3 hr, 6 hr post dose)		X k (pre- dose, 1 hr, 2 hr, 3 hr, 6 hr post dose)		X ^k (pre-dose, 1 hr, 2 hr, 3 hr, 6 hr post dose)		Х	
Blood sample for cGMP assay (target engagement)		X k (0hr, 1 hr, 2 hr, 3 hr, 6 hr)	X k (pre-dose, 1 hr, 2 hr, 3 hr, 6 hr post dose)		X k (pre-dose, 1 hr, 2 hr, 3 hr, 6 hr post dose)		X ^k (pre-dose, 1 hr, 2 hr, 3 hr, 6 hr post dose)		X	
Spot urine sample for cGMP		Х	X		X		Х		X	
6 hr urine collection for cGMP		X	X		X		X			
Echocardiogram	X									_
Dispense study drug			X m		X ^m		X ^m			
Return study drug					X n		X n		X n	

[figure not shown]
CONFIDENTIAL

FINAL 10 AUG 2022 Page 70 of 73

[figure not shown]
Abbreviations: AE = adverse event; aPTT: activated partial thromboplastin time; cGMP = cyclic guanosine monophosphate; ECG = electrocardiogram; ET = end of trial; FSH = follicle-stimulating hormone; hr = hour; INR = international normalized ratio; PK = pharmacokinetics; PT = prothrombin time

- a. All assessments will be performed pre-dose unless otherwise specified.

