- b. All screening laboratory tests should ideally be performed on Day -15 to ensure eligibility assessment completed during screening window. In rare situations, if the laboratory reporting is delayed due to unforeseen circumstances (e.g., transit delays, lost sample, or outstanding queries), up to 21 days of screening will be accepted.
- c. Women of childbearing potential only.
- d. FSH will only be measured for women <55 years of age who have not had a menstrual period for ≥12 months at screening.
- e. Vital signs, including heart rate, blood pressure (systolic and diastolic), respiratory rate, and temperature, will be measured at the time-points specified in the above table and at all unscheduled visits as applicable. Vital sign measurements will be recorded with the subject in a seated position and after the subject has been resting for at least 5 minutes. All measurements will be performed singly. For any abnormal vital sign finding, further assessment should be performed as deemed necessary by the investigator. In case of re-screening, all vital sign parameters will be rechecked as described above.
- f. Physical examination will include assessment of heart, lung, extremities, body weight, and height. Height will only be assessed at screening. Body weight will be assessed at screening and at Visit 9. All the other assessments will be performed at all the applicable time-points and at all unscheduled visits as applicable.
- g. Resting 12-lead ECGs will be recorded at the time-points specified in the above table and at all unscheduled visits as applicable. Resting 12-lead ECGs will be recorded after the subject has been supine and at rest for at least 5 minutes.
- h. The blood sample will be collected 12-24 hours after last dose of study drug.
- i. Laboratory safety tests will include biochemistry, urinalysis, and hematology. Please refer to Appendix 2 for the specific analytes of each test. Laboratory safety tests will be performed at the time-points specified in the above table and at all unscheduled visits as applicable. All laboratory safety tests will be analyzed at a central laboratory.
- j. On the days of Visit 5 and Visit 7, subjects will be instructed NOT to take their dose of study drug before the pre-dose blood and urine sampling. Subjects will not take the study drug at Visit 9. They will be instructed to take the study drug through the day before Visit 9.

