## 5. Data Handling

#### 5.1. Time Points and Visit Windows

#### 5.1.1. General Definitions

All assessment days will be related to the day of first dose of treatment.

Day 1 is defined as first dose of treatment. Relative days after Day 1 are calculated as (assessment date – Day 1 date) + 1. Relative days prior to Day 1 are calculated as (assessment date – Day 1 date). The day prior to Day 1 is Day -1. Day 0 is not defined.

The date of the first dose of treatment for each subject will be taken from the *Study Drug Administration (Oral)* eCRF page at Visit 3. If the date in this eCRF page is missing, alternatively the date of randomization + 1 will be used.

**The date of the last dose of treatment** for each subject will be taken from the *End of Treatment* eCRF page. If the date in this eCRF page is missing, alternatively the Completion or discontinuation date of *Disposition – End of Study* eCRF form will be used. If the date is missing because the subject was lost to follow-up, the date of the last visit will be imputed, if appropriate.

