#### 5.1.5. Visit Windows

Table 4 Definition of Visit Windows for Efficacy and Safety Assessments provides the relative trial day ranges to be applied to the assessment / sample collection date to derive the analysis visits for analyses of trial assessments.

The following considerations are to be followed when deriving the analysis visit:

- The relative day number of the assessment lies between the lower and upper boundary of the analysis visit window (the boundary values are included)
- Both scheduled and unscheduled assessments are included for visit windowing
- If there are two or more valid assessments for a defined window the following rules will be applied:

CONFIDENTIAL

- CONFIDENTIAL
  Protocol Reference: CRD-740-201
- If there are multiple assessments with non-missing assessment results for any specified analysis visit window, the assessment that is closest to the target day of analysis window will be used for analysis
- If there are two or more assessments with non-missing results and the same distance to the planned study day, the assessment prior to the planned study day will be used for analysis.

Table 4 Definition of Visit Windows for Efficacy and Safety Assessments Part A

Visit	Target Day of Visit a	Protocol Visit Windows	Analysis Visit Window	Target Day of Analysis Visit	Analysis Visit
Screening (Day -15 to Day -2)	Day -15	Day -15 to Day -2	Day -21 to Day -2	Day -15	Screening
Visit 2, Day -1	Day -1	Day -1			Day -1
Visit 3, Day 1	Day 1	Day 1	Day 1	Day 1	Baseline*
Visit 4, Day 3 (remote)	Day 3	Day ± 1	NA		
Visit 5, Day 15	Day 15	Day ± 2	Day 2 to Day 24	Day 15	Week 2
Visit 6, Day 17 (remote)	Day 17	Day ± 1	NA		
Visit 7, Day 29	Day 29	Day ± 3	Day 25 to Day 43	Day 29	Week 4
Visit 8, Day 57 (remote)	Day 57	Day ± 5	NA		
Visit 9, Day 85	Day 85	Day ± 5	Day 71 to Day 99	Day 85	Week 12
Visit 10, Day 113 (remote)	Day 113	Day – 2/ + 5	NA		

<sup>a Relative to first dose of treatment

NA= Not Applicable

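### Minor: the permitted visit windows let the last scheduled AE contact (Visit 10) fall 22 to 27 days after a completer's last dose, short of the 28-day AE reporting period

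*Protocol*

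**What the plan says.** - **Reporting period.** Protocol Appendix 1: "AE reporting begins from the time of informed consent and ends 28 days after the last dose of study drug".
- **Visit 9.** The Part A schedule in Appendix 4 sets it at "Day 85 or ET (Week 12) (±5 days").
- **Last dose.** Footnote j to that schedule says no drug is taken on the Visit 9 day, and of completers: "They will be instructed to take the study drug through the day before Visit 9".
- **Visit 10.** The schedule sets it at "Day 113 (Week 16) (-2/+5 days"). It is the last column with AE recording marked. Under protocol section 3.2, attending it completes the study.
- **Day count.** SAP 5.1.1: "All assessment days will be related to the day of first dose of treatment". SAP Table 4 lists "Visit 10, Day 113 (remote") with the same -2/+5 window and no analysis window (NA).
- **Duty outside visits.** Protocol section 7.2.1: "The investigator and any designees are responsible for detecting, documenting, and reporting events that meet the definition of an AE or SAE". Section 7 adds: "Please refer to the study-specific safety guidance documents for detailed safety requirements of this study". That guidance is not public.

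**The concern.** The end of AE reporting is counted from last dose, while the visit that should close it is counted from first dose. If Visit 9 is late or Visit 10 is early, the last scheduled contact can come before the reporting period ends. Each deviation is within its own window, and the visible text has no rule steering the site to the later Visit 10 days.

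In Appendix 1, asking about AEs is tied to visits. Its 28-day follow-up rule reaches events already ongoing at discontinuation or arising before the final follow-up visit, and the active phase closes at the follow-up visit. A new event after an early Visit 10 is therefore reportable, but no scheduled contact would elicit it.

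Safety is a primary objective of Part A. The population-level summary in SAP 3.1.2.5 includes the proportions of subjects with any AE and with any SAE, and the treatment-emergent definition in SAP 6.7.2 states no end date. A missed late event could therefore bear on those proportions. The exposure-adjusted rates are not at risk, because their denominator is exposure time.

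**Working it through.** The 28 days is a stated rule, so there is no derived figure to reproduce. The check is day arithmetic.

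**Inputs**
- Visit 9 (V9): Day 85 ± 5 = Day 80 to 90 (Appendix 4).
- Last dose for a completer: V9 − 1 = Day 79 to 89 (footnote j).
- Visit 10 (V10): Day 113 −2/+5 = Day 111 to 118 (Appendix 4).
- Required coverage: 28 days after last dose (Appendix 1).

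**Formula.** Interval = V10 − (V9 − 1).
- On target days: 113 − 84 = 29 days.
- Minimum: 111 − 89 = 22 days.
- Maximum: 118 − 79 = 39 days.

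**All permitted pairs** (11 Visit 9 days × 8 Visit 10 days = 88). The 28-day floor for Visit 10 is (V9 − 1) + 28 = V9 + 27.

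| Visit 9 day | Interval over V10 = Day 111 to 118 | 28-day floor for V10 | V10 days short of 28 |
|---|---|---|---|
| 80 to 84 | 32–39 (Day 80) down to 28–35 (Day 84) | Day 107 to 111 | 0 of 8 each |
| 85 | 27–34 | Day 112 | 1 of 8 |
| 86 | 26–33 | Day 113 | 2 of 8 |
| 87 | 25–32 | Day 114 | 3 of 8 |
| 88 | 24–31 | Day 115 | 4 of 8 |
| 89 | 23–30 | Day 116 | 5 of 8 |
| 90 | 22–29 | Day 117 | 6 of 8 |

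Short pairs: 1 + 2 + 3 + 4 + 5 + 6 = 21 of 88. By interval, 22, 23, 24, 25, 26 and 27 days occur in 1, 2, 3, 4, 5 and 6 pairs. Exactly 28 days occurs in 7 pairs and 29 to 39 days in 60 (21 + 7 + 60 = 88).

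**Alternative anchor.** If sites timed Visit 10 from the actual Visit 9 (+28 days, −2/+5), the interval would be 28 − 2 + 1 = 27 to 28 + 5 + 1 = 34 days. A one-day shortfall would still be possible.

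**The case against.** The strongest reply is that two different things are being compared. Appendix 1 says how long AEs are reportable; it does not require a scheduled contact on or after day 28. The investigator's duty in section 7.2.1 continues, subjects are encouraged to report voluntarily during the study, and no stated rule is broken. This is correct, and it is why the point is minor. It does not remove the gap: a site can follow the schedule exactly, complete the subject at Visit 10, and stop asking before the protocol's own period ends.

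Second, the planned schedule works, and 22 days is a single pair out of 88, with Visit 9 fully late and Visit 10 fully early. That stands too. Visit 10 is booked once Visit 9 is known, so treating the two days as freely paired is a worst case, and how many subjects would be affected is unknown. But extremes are not needed: an on-time Visit 9 with Visit 10 on Day 111 already falls one day short.

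Third, the SAP's day count governs analysis, not site booking. This weakens the 22-day figure somewhat, although Day 113 naturally reads from Day 1.

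Fourth, section 3.1 and parts of the schedule are not visible, and sections 7 and 7.2.2 defer to guidance that is not public. An instruction to sites may exist there. This limits confidence and cannot be resolved from the documents.

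Finally, an amendment may seem heavy when the existing window already permits compliance and no other amendment is evident; SAP 2.1 says Part B will not be conducted. That bears on how the change is made, not on whether the gap exists.

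**Conclusion.** The concern holds as a minor design point. It affects only completers whose Visit 9 falls on Day 85 or later, and at most 6 off-treatment days per subject.

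The conclusion assumes that both windows are counted from Day 1, that completers take their last dose the day before Visit 9 as instructed, and that no unseen text already times Visit 10 from last dose. Confidence is medium because of that last assumption.

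**What to change.** Keep Visit 10 at Day 113 (−2/+5) and add to the schedule: *and, for subjects who complete treatment, no earlier than 28 days after last dose.* The latest permitted last dose gives 89 + 28 = Day 117, inside the window that closes on Day 118, so the clause can always be met. Of the 88 pairs, 88 − 21 = 67 remain permitted, with intervals of 28 to 39 days.

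Do not instead shorten the active phase or the follow-up cut-off in Appendix 1. Early stoppers are asked to stay for the remaining visits (protocol 4.3.3), SAP Table 3 uses their later data under a treatment policy strategy, and most permitted Visit 10 days fall after day 28 anyway. If those sentences are edited for another reason, end them at the later of Visit 10 and last dose + 28 days.

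**Cost.** The change is one clause, but it is a protocol amendment needing IRB/EC approval (Appendix 3), and SAP Table 5 lists ten countries. It is best bundled with another amendment. Sites must check the last-dose date when booking. The permitted Visit 10 days fall to 7, 6, 5, 4, 3 and 2 of 8 when Visit 9 is on Day 85, 86, 87, 88, 89 and 90. The latest permitted Visit 10 does not move, so neither does the limit on last-subject-last-visit. SAP Table 4 stays correct and no analysis changes. In the visible schedule, Visit 10 is remote and records only AEs and concomitant medications.
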